13.1 Primary Analysis

The primary efficacy endpoints of the study are:

- Mean change from baseline in post-CAE® inferior corneal fluorescein staining score on the Ora Calibra® scale at Visit 5 (Day 29), comparing [REDACTED] K-161 [REDACTED] to vehicle [REDACTED]
- Mean change from baseline in post-CAE® ocular discomfort scale on the Ora Calibra® scale at Visit 5 (Day 29), comparing [REDACTED] K-161 [REDACTED] to vehicle [REDACTED]

Change from baseline for both endpoints will be calculated as Visit – Baseline, where a positive difference indicates a worsening of dry eye signs or symptoms and a negative difference indicates an improvement of dry eye signs or symptoms. Treatment comparisons between [REDACTED] K-161 [REDACTED] and vehicle [REDACTED] will be calculated as [REDACTED] K-161 [REDACTED] - vehicle [REDACTED]. All primary endpoints will be described in subject listings.

13.1.1 INFERIOR CORNEAL FLUORESCEIN STAINING SCORE AT VISIT 5 (DAY 29) POST-CAE, [REDACTED] K-161 [REDACTED] VS VEHICLE [REDACTED]

Fluorescein staining will be conducted at all visits at pre-CAE® and post-CAE®. Grading will be conducted using the Ora Calibra® Scale from 0 to 4 with the use of half grade (0.5) increments, where grade 0 = None and 4 = Severe. The regions to be assessed will be the central, superior, inferior, temporal, nasal, corneal sum, conjunctival sum, and total eye score for study eye only.

Inferior corneal fluorescein staining will be summarized at Visit 5 (Day 29) Post-CAE® by treatment groups using continuous descriptive statistics. Primary analysis will use an analysis of covariance (ANCOVA) model adjusted for baseline value, site, and with treatment group as the explanatory variable. Changes from baseline for each treatment group in inferior corneal fluorescein staining will be compared between [REDACTED] K-161 [REDACTED] and vehicle [REDACTED]. In addition, treatment by baseline and treatment by study site interactions will be explored in separate models to evaluate how the treatment effect may differ for baseline value and study sites. Analyses will be performed by baseline stratification (≤ 3.0 and >3.0) and/or site to understand how the treatment effect differs for baseline value and study sites. Least squares (LS) means for each treatment group and the LS mean difference between treatment groups will be presented from the models together with standard errors (SE), two-sided p-values, and two-sided 95% CIs.

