Tipping point analyses will be included for further sensitivity analyses. The SAS® procedure `PROC MI` will be used to impute non-monotone missing data using MCMC to obtain 100 complete datasets with a monotone missing pattern as described for the control-based pattern mixture model imputation. Then, the monotone datasets will be imputed using a set of shift values for the active treatment group. The set of shift values for the imputation will be from 0 to 4 by 0.1 increments. The SAS® code for obtaining the imputed data is:

```

PROC MI DATA = INDATA SEED = 935769 OUT = MDATA NIMPUTE = 100
      MINIMUM = 0 MAXIMUM = 4 ROUND = 0.5;
      BY TREATMENT;
      MCMC IMPUTE=MONOTONE;
      VAR BASELINE IFS4 IFS5;
      RUN;

PROC MI DATA = MDATA SEED = 427586 OUT = OUTDATA NIMPUTE = 1
      MINMAXITER = 1000000 MINIMUM = . 0 0 0 MAXIMUM = . 4 4 4
      ROUND = . 0.5 0.5 0.5;
      BY _Imputation_;
      CLASS TREATMENT;
      MONOTONE REG (IFS5 = BASELINE IFS4/DETAILS);
      MONOTONE REG (IFS4 = BASELINE /DETAILS);
      MNAR ADJUST (IFS5/ SHIFT = X ADJUSTOBS = (TREATMENT = 'ACTIVE
      TREATMENT') );
      VAR BASELINE IFS4 IFS5;
      RUN;

```

where

- *INDATA* is the name of the input dataset
- *MDATA* is the name an intermediary dataset with a monotone missing pattern
- *OUTDATA* is the name of the output dataset

- *TREATMENT* is the name of the treatment group variable
- *BASELINE* is the baseline inferior corneal fluorescein staining
- *IFS4-IFS5* are the inferior corneal fluorescein staining at Visits 4 (Day 15) through Visit 5 (Day 29)
- *X* is the shift parameter within the set of shift parameters [0 to 4 by 0.1]

Least squares mean differences, SEs, two-sided CIs and p-values will be reported for each shift value.

Further, primary efficacy analyses will be performed with the PP population with observed data only for sensitivity analysis. The following SAS® code is an example of the ANCOVA model for observed data, LOCF, and PP analyses:

```
PROC MIXED;
  CLASS TREATMENT SITE;
  MODEL CHG = BASELINE TREATMENT SITE / SOLUTION COVB;
  LSMEANS TREATMENT / CL PDIFF;
RUN;
```

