The primary analysis will use control-based pattern mixture model imputation on the ITT population at Visit 5 (Day 29). SAS® code for the multiple imputation analysis will resemble the code in Section 13.1.1 for inferior corneal fluorescein staining. The random number seeds for the monotone imputation and pattern mixture model imputation described in Section 13.1.1 will be SEED = 354846 and SEED = 956546, respectively. In addition, the rounding parameter will be ROUND = 1.

Should control-based pattern mixture model imputation fail to produce the required imputations, baseline measurements of overall ocular discomfort, burning, dryness, grittiness, and stinging from the Ora Calibra® Ocular Discomfort & 4-Symptom Questionnaire will be added to the VAR statement in an iterative fashion until imputation is successful. If multiple imputation still fail to generate the required imputations, then MINIMUM, MAXIMUM, and ROUND statements will be removed.

Sensitivity analyses will be performed using on the ITT population using observed data only and ITT population using LOCF.

Sensitivity analyses under the assumption of a missing at random mechanism will be performed using MCMC imputation on the ITT population as described in section 13.1.1 except the random number seed for PROC MI will be SEED = 146645 and the rounding parameter will be ROUND = 1.

Should MCMC imputation fail to produce the required imputations, baseline measurements of overall ocular discomfort, burning, dryness, grittiness, and stinging from the Ora Calibra® Ocular Discomfort & 4-Symptom Questionnaire will be added to the VAR statement in an iterative fashion until imputation is successful. If MCMC multiple imputation still fail to generate the required imputation, then MINIMUM, MAXIMUM, and ROUND statements will be removed.

Tipping point analysis will be included for further sensitivity analyses in the manner described in section 13.1.1. Then, the monotone datasets will be imputed using a set of shift values for the active treatment group. The random number seeds for the monotone imputation and pattern mixture model imputation described in Section 13.1.1 will be SEED = 5324652 and SEED = 236135, respectively. The set of shift values for the imputation will be from 0 to 4.0 by 0.1 increments. The MINIMUM, MAXIMUM, and ROUND statements will be removed.

Further, primary efficacy analyses will be performed with the PP population with observed data only for sensitivity analysis.

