Tipping point analysis will be included for further sensitivity analyses in the manner described in section 13.1.1 on the ITT population. The random number seeds for the monotone imputation and pattern mixture model imputation described in Section 13.1.1 will be SEED = 231219 and SEED = 981982, respectively.

The set of shift values for the imputation will be from 0 to -5 by an increment of -0.25. The MAXIMUM, MINIMUM and ROUND statements will be removed.

Further, primary efficacy analyses will be performed with the PP population with observed data only for sensitivity analysis.

Two sample t-tests will be conducted as sensitivity analyses using pattern mixture model imputation with the ITT population, observed data only with the ITT population, LOCF imputation with the ITT population, MCMC imputation with the ITT population, and observed data only with the PP population. Wilcoxon rank sum tests will be conducted as sensitivity analyses using observed data only with the ITT population, LOCF imputation with the ITT population, and observed data only with the PP population.

Sensitivity analyses will be performed on the ITT and PP populations using observed data only, and on the ITT population using LOCF methodology.

Least squares means for unanesthetized Schirmer's test changes from baseline at Visit 5 (Day 29) will be displayed graphically in a bar chart with 95% CI bars by treatment group based on the ANCOVA analysis of the multiple pattern mixture model imputation of the ITT population.

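### The staining tipping-point step keeps the 0-4 limits while shifting by up to 4, unlike the ODS step, so its nominal shifts may be only partly applied and its shift labels may not be comparable

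*SAP*

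**What the plan says.** SAP 13.1.1 grades staining on the Ora Calibra "Scale from 0 to 4 with the use of half grade (0.5) increments". Change is follow-up minus baseline, "where a positive difference indicates a worsening of dry eye signs or symptoms", so a positive shift penalises the active arm.

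For the staining tipping point:
- Grid: "The set of shift values for the imputation will be from 0 to 4 by 0.1 increments".
- Variable shifted: the Day 29 score, in active-arm subjects ("MNAR ADJUST (IFS5/ SHIFT = X ADJUSTOBS = (TREATMENT = 'ACTIVE").
- Limits in that same PROC MI step: "MINMAXITER = 1000000 MINIMUM = . 0 0 0 MAXIMUM = . 4 4 4".
- Rounding in that step: "ROUND = . 0.5 0.5 0.5".
- Output: LS mean difference, SE, CI and p-value at every nominal shift. Nothing is planned on the shift achieved.

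The ODS tipping point (SAP 13.1.2) also concerns a 0-4 score and uses a 0 to 4.0 grid in steps of 0.1. There the instruction is "The MINIMUM, MAXIMUM, and ROUND statements will be removed". The Schirmer's and TFBUT tipping points (SAP 13.2.1 and 13.2.2) say "The MAXIMUM, MINIMUM and ROUND statements will be removed".

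SAP 13.1.1 has a rule that eventually drops the limits and rounding if imputation fails. It is written for the control-based pattern-mixture imputation and for the MCMC imputation, not for the tipping-point step.

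**The concern.** A tipping-point table is read by its shift column: the reader looks for the penalty at which significance is lost and judges whether that penalty is plausible. This works only if the labelled penalty is the one applied. Here the grid is as wide as the scale and the code holds imputed values inside the scale. If the limits act on the shifted value, a score near 2.5 cannot move by 3 or 4.

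At stake is the meaning of the shift column for the first-ranked endpoint. A tip at a nominal 3.8 could be read as a 3.8-point penalty when little more than 1 point was applied. The ODS table, with an identical grid, would mean something different.

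**Working it through.** **1. The plan's own figure.** With SD 0.77, difference 0.46, 60 per arm and two-sided 0.05 (SAP 5), the noncentrality is (0.46/0.77) × √(60/2) = 3.27 and the t-test power is 0.901. The stated 90% is reproduced and is not affected by this point. The documents give no figure for the tipping point itself.

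**2. Assumptions.** The documents give no Day 29 means, imputation SD or missingness. I take an unshifted imputed mean μ of 2.0 to 3.0. I take an imputation SD σ of 0.5 to 0.77; 0.77 is the SAP's SD of change, and a residual SD given baseline and Day 15 could be smaller. I assume that a shifted draw outside 0-4 is redrawn and that MINMAXITER caps the attempts.

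**3. Shift achieved.** With m = μ + s, a = (0 − m)/σ and b = (4 − m)/σ, the mean of the accepted draw is E(m) = m + σ[φ(a) − φ(b)]/[Φ(b) − Φ(a)]. The shift achieved is E(μ + s) − E(μ).

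Example: μ = 2.5, σ = 0.77, s = 4. Then m = 6.5, b = −3.25 and E = 3.795. Unshifted, E = 2.454. The achieved shift is 3.795 − 2.454 = 1.34.

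| μ, σ | nominal 1 | 2 | 3 | 4 |
|---|---|---|---|---|
| 2.0, 0.5 | 0.97 | 1.60 | 1.81 | 1.89 |
| 2.0, 0.77 | 0.85 | 1.39 | 1.64 | 1.76 |
| 2.5, 0.77 | 0.71 | 1.08 | 1.25 | 1.34 |
| 3.0, 0.77 | 0.53 | 0.78 | 0.90 | 0.97 |
| 3.0, 0.5 | 0.63 | 0.84 | 0.92 | 0.95 |

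At nominal 4 the share achieved runs from 0.95/4 = 24% to 1.89/4 = 47%. Adding half-point rounding changes little (μ = 2.5, σ = 0.77: 0.72, 1.10, 1.28, 1.38). Clipping at 4 instead of redrawing gives 0.89, 1.39, 1.50, 1.51. Either way the upper grid flattens towards a score of 4.

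**4. Redraws.** The expected number of draws per value is 1/[Φ(b) − Φ(a)]. At shift 4 it is about 1,700 for μ = 2.5, σ = 0.77. It is about 3.5 million for μ = 3.0, σ = 0.6 and for μ = 2.5, σ = 0.5. In those two cases the chance that 1,000,000 attempts all fail is about exp(−1/3.49) = 0.75 per value. At μ = 3.0, σ = 0.5 the acceptance probability is about 1e-9, so failure is nearly certain.

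**5. Effect on the tipping shift.** This used a simplified simulation: 60 per arm, SD 0.77, observed difference 0.46, equal missingness in both arms, imputation from the pooled mean, 100 imputations combined by Rubin's rules, and a t-test. The table gives the first nominal shift at which p exceeds 0.05.

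| Missing | Limits kept (vehicle mean 2.0 / 2.5 / 3.0) | Limits removed |
|---|---|---|
| 5% | none up to 4 | 2.3-2.4 |
| 10% | 1.3 / 1.8 / 3.8 | 1.1 |
| 15% | 0.6 / 0.8 / 1.1 | 0.5-0.6 |
| 20% | 0.4 / 0.4 / 0.6 | 0.3 |

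**6. What a result that never tips means.** At 5% missing and vehicle mean 2.5, the limited run still has p = 0.017 at nominal 4. The unlimited run tips at 2.3. The pooled unshifted mean is (2.50 + 2.04)/2 = 2.27, so that tip implies an imputed mean of about 4.6, which is off the scale.

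**The case against.** **The mechanism is inferred.** The SAP never says that the limits act on the shifted value. If they act on the unshifted draw, the shift is applied in full and step 3 does not apply; the limits would then merely keep the unshifted draw on the scale, as in the primary imputation. MINMAXITER is raised in this step alone, which suggests that the limits were expected to bind, but it is not proof. This objection stands, and the figures are conditional on it.

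**Robustness is not shown to be overstated.** A reader might infer that keeping the limits makes the primary sign look more robust than it is. The documents do not support that. Under redrawing, the analysis converges on 4, the worst attainable score. With a mean of 2.5 the most that values could worsen on average is 1.5, so an achieved 1.34 is close to the maximum. What is inflated is the label.

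**Only ODS is a true comparator.** Schirmer's and TFBUT also drop the limits in their primary imputation, and their shifts are negative and on other grids. ODS keeps the limits in its primary imputation and drops them for the tipping point, so there the removal is specific to this step. The contrast with ODS is enough.

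**Removing the limits has its own cost.** With mean 2.5 and SD 0.77, the share of shifted values above 4 is 26% at shift 1, 74% at shift 2 and over 99.9% at shift 4. The choice is between an imprecise label and impossible scores. Either is defensible if declared.

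**Conclusion.** The inconsistency with ODS is certain from the text, and no reason is given for it. Its effect is conditional. If the limits act after the shift, nominal shifts above about 1 to 2 are only partly applied, and a nominal 4 delivers about 0.95-1.9 under the assumed means and SDs. The upper grid then repeats nearly one worst-score scenario, and at high means or small SDs the step may fail with no stated fallback. In the simplified simulation the inflation of the tipping shift is large at 5-10% missing and small at 20%.

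Two stronger readings should be set aside: that large shifts are certainly not applied (the order of operations is unstated), and that a result which never tips is falsely reassuring (it would have survived near-worst attainable scores). This is one sensitivity analysis among several. The primary estimate, the testing hierarchy, Type I error and power are unaffected.

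**What to change.** Choose one of two options in SAP 13.1.1 and say why.

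1. Remove MINIMUM, MAXIMUM, ROUND and MINMAXITER from the second PROC MI step of the staining tipping point, as for ODS. This is a one-line code change. Labels become exact and comparable with ODS, but most imputed values exceed 4 at large shifts, which the ODS analysis already accepts.
2. Keep the limits. State whether they act before or after the shift, report the mean imputed score and mean shift achieved beside each nominal shift, and extend the existing rule that drops the limits on imputation failure to this step. This costs two table columns and two sentences.

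If the second option is taken, also check the option lists: MINIMUM, MAXIMUM and ROUND each have four entries, while the VAR statement names three variables.

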13.2 Important Secondary Analyses

13.2.1 UNANESTHETIZED SCHIRMER'S TEST AT VISIT 5 (DAY 29), [REDACTED] K-161 [REDACTED] vs VEHICLE [REDACTED]

Unanesthetized Schirmer's test will be conducted at all visits at pre-CAE®. The Schirmer's test strip will be placed in the lower temporal lid margin of each eye. After 5 minutes, the test strip will be removed and the length of the moistened area will be recorded in mm for each eye. Lower values indicate less tears produced in the eye. Analyses will only be produced for study eye.

Unanesthetized Schirmer's test will be summarized at Visit 5 (Day 29) Pre-CAE® by treatment groups using continuous descriptive statistics. Primary analysis will use an ANCOVA model adjusted for baseline unanesthetized Schirmer's test, site and with treatment group as the explanatory variable. Changes from baseline for each treatment group in ocular discomfort will be compared between [REDACTED] K-161 [REDACTED] and vehicle [REDACTED]. In addition, treatment by baseline and treatment by study site interactions will be explored in separate models to evaluate how the treatment effect may differ for baseline value and study sites. In the case of a significant interaction at the 0.05 level, analyses will be performed by baseline median stratification and/or site to understand how the treatment effect differs for baseline value and study sites. Least squares means for each treatment group and the LS mean difference between treatment groups will be presented from the models together with SE, two-sided p-values, and two-sided 95% CIs.

The primary analysis will use control-based pattern mixture model imputation with the ITT population. The random number seeds for the monotone imputation and pattern mixture model imputation described in Section 13.1.1 will be SEED = 465485 and SEED = 849159, respectively. The MINIMUM, MAXIMUM, and ROUND statements will be removed.

Sensitivity analyses will be performed using on the ITT population using observed data only and ITT population using LOCF.

Sensitivity analyses under the assumption of a missing at random mechanism will be performed using MCMC imputation on the ITT population as described in section 13.1.1 except the random number seed for PROC MI will be SEED = 884564 and the MINIMUM, MAXIMUM, and ROUND statements will be removed.

Tipping point analysis will be included for further sensitivity analyses in the manner described in section 13.1.1 on the ITT population. The random number seeds for the monotone imputation and pattern mixture model imputation described in Section 13.1.1 will be SEED = 231219 and SEED = 981982, respectively.

The set of shift values for the imputation will be from 0 to -5 by an increment of -0.25. The MAXIMUM, MINIMUM and ROUND statements will be removed.

Further, primary efficacy analyses will be performed with the PP population with observed data only for sensitivity analysis.

Two sample t-tests will be conducted as sensitivity analyses using pattern mixture model imputation with the ITT population, observed data only with the ITT population, LOCF imputation with the ITT population, MCMC imputation with the ITT population, and observed data only with the PP population. Wilcoxon rank sum tests will be conducted as sensitivity analyses using observed data only with the ITT population, LOCF imputation with the ITT population, and observed data only with the PP population.

Sensitivity analyses will be performed on the ITT and PP populations using observed data only, and on the ITT population using LOCF methodology.

Least squares means for unanesthetized Schirmer's test changes from baseline at Visit 5 (Day 29) will be displayed graphically in a bar chart with 95% CI bars by treatment group based on the ANCOVA analysis of the multiple pattern mixture model imputation of the ITT population.

13.2.2 TEAR FILM BREAK UP TIME

The TFBUT will be recorded at all visits at pre-CAE® and post-CAE®. For each eye, 2 measurements will be taken and averaged unless the 2 measurements are >2 seconds apart and are each <10 seconds, in which case, a third measurement would be taken and the 2 closest of the 3 would be averaged. This average will then be used for analyses. Analyses will be provided for study eye only.

Tear Film Break Up Time will be summarized at Visit 5 (Day 29) Post-CAE® by treatment groups using continuous descriptive statistics. Primary analysis will use an ANCOVA model adjusted for baseline TFBUT, site and with treatment group as the explanatory variable. Changes from baseline for each treatment group in TFBUT will be compared between [REDACTED] K-161 [REDACTED] and vehicle [REDACTED]. In addition, treatment by baseline and treatment by study site interactions will be explored in separate models to evaluate how the treatment effect may differ for baseline value and study sites. In the case of a significant interaction at the 0.05 level, analyses will be performed by baseline median stratification and/or site to understand how the treatment effect differs for baseline value and study sites. Least squares means for each treatment group and the LS mean difference between treatment groups will be presented from the models together with standard errors SE, two-sided p-values, and two-sided 95% CIs.

The primary analysis will use control-based pattern mixture model imputation with the ITT population. The random number seeds for the monotone imputation and pattern mixture model imputation described in Section 13.1.1 will be SEED = 5466765 and SEED = 903573, respectively. The MINIMUM, MAXIMUM, and ROUND statements will be removed.

Sensitivity analyses will be performed using on the ITT population using observed data only and ITT population using LOCF.

Tipping point analysis will be included for further sensitivity analyses in the manner described in section 13.1.1. Then, the monotone datasets will be imputed using a set of shift values for the active treatment group. The set of shift values for the imputation will be from 0 to -2 by an increment of -0.1. The random number seeds for the monotone imputation and pattern mixture model imputation described in Section 13.1.1 will be SEED = 392187 and SEED = 748451, respectively. The MAXIMUM, MINIMUM and ROUND statements will be removed.

Sensitivity analyses under the assumption of a missing at random mechanism will be performed using MCMC imputation on the ITT population as described in section 13.1.1 except the random number seed for PROC MI will be SEED = 234993 and the MINIMUM, MAXIMUM, and ROUND statements will be removed.

Two sample t-tests will be conducted as sensitivity analyses using pattern mixture model imputation with the ITT population, observed data only with the ITT population, LOCF imputation with the ITT population, MCMC imputation with the ITT population, and observed data only with the PP population. Wilcoxon rank sum tests will be conducted as sensitivity analyses using observed data only with the ITT population, LOCF imputation with the ITT population, and observed data only with the PP population.

Least squares means for TFBUT changes from baseline pre-CAE® and post-CAE® at Visit 5 (Day 29) will be displayed graphically in a bar chart with 95% CI bars by treatment group based on the ANCOVA analysis of the multiple pattern mixture model imputation of the ITT population.

